At home: Participants will be received a weekly recommendation for points that tailored for their weekly symptoms experience and instructed to press the tape and seeds covering each ear point for 10 seconds per time for 3 times/point four times daily (morning, afternoon, evening and before bed), even when they do not experience fatigue. The optimal pressure is considered to have been achieved when the participants feel localized tingling or mild discomfort. The tape and seeds will remain on ear points for 5 days. Participants will be instructed to remove both at the end of the 5th day and apply the new seeds.

To ensure the accuracy of the ear points, participants will be asked to send the photo of their ear after the seeds are placed for comments and suggestions.

The combined Acupressure and TEHE program (TEHE plus): In addition to the TEHE program, participants will receive Acupressure training at the first study visit and weekly recommendations that include both exercise goal and suggested pressure points.

The combined MBI and TEHE program: In addition to the TEHE program, the TEHE+MBI group will receive a 10-15 min audio-recording of a mindfulness-based body scan or mindful movement or mindful breathing. This technique is often used as an entry point to mindfulness

meditation.^{45, 46} This recording guided the participants to focus on specific bodily and breathing sensations.

At home: Participants will be instructed to include mindfulness-based body scan or mindful breathing, mindful movement. The participant will be instructed to acknowledge all sensation with the non-judgemental acceptance and not attempting to change the experience. Participants will receive a weekly recommendation for the activity goals and suggested mindfulness techniques.

Control Group: The control group will receive instructions on how to use the physical activity tracker and the smartphone application. Participants will be asked to meet with a research team member on the first week to review the equipment set up instruction. Participants will be asked to monitor their physical activity daily using Fitbit and receive a daily notification to complete the short on fatigue and other symptoms from the smartphone application.

Dependent variables and instruments. The study variables will be measured as follows:

Questionnaires

- *Fatigue* will be measured by the Functional Assessment of Cancer Therapy-Fatigue subscale (FACT-F). A 13-item questionnaire with good test-retest reliability ($r = 0.90$), internal consistency ($\alpha = 0.93$ and 0.95) on initial and test-retest administration suggesting that it can be administered as an independent, unidimensional measure of fatigue.²⁵ and the Patient-Reported Outcome Measurement Information System short form-Fatigue (PROMIS-F) 6-items; self-reported fatigue (frequency, duration, intensity) and the impact of physical, mental, & social activities influencing one's daily lives, including work & social roles; has five response options (1 or never to 5 or always). Initial psychometric properties showed an internal consistency reliability coefficient of greater than 0.80.
- *Self-perceived cognitive dysfunctions* were measured by the 38-item Multiple Ability Self-Report Questionnaire (MASQ) in 5 domains: language, visual-perceptual ability, verbal memory, visual-spatial memory, and attention/ concentration, using a 1-5 Likert scale rating.⁴⁷ The language subscale includes items relating to speech, the ability to follow conversations, and the ability to convey thoughts. Visual perceptual ability items measure the patient's ability to follow visual directions and solve puzzles. Items in the verbal memory subscale evaluate forgetfulness with events, important information, and names, and visual-spatial memory items relate to faces, pictures, and places. The attention/concentration subscale items assess perceived difficulties with performing tasks, simple calculations, alertness, and maintaining a train of thought. The total score for each domain ranged from 8-40, except for visual-perceptual ability, which ranged from 6-30.⁴⁸ Higher MASQ scores indicate a greater perception of cognitive dysfunctions. Each MASQ subscale had high internal consistency reliability (Cronbach's coefficient alpha ranging from 0.72-0.74).⁴⁷
- *Psychosocial factors contributing to fatigue* (e.g., physical function, anxiety, depressive symptom, sleep disturbance, pain intensity, pain interference, and ability to participate in the social activities) will be measured by the Patient-Reported Outcome Measurement Information System (PROMIS)-Adult Profile short form. The items were rated on the past seven days using a 5-point response scale from "never" to "almost always." Initial psychometric properties showed an internal consistency reliability coefficient of greater than 0.80. Disease stage, PSA, and testosterone levels will be obtained by chart review.

Date: September 26, 2024

Principal Investigator: [name]

Application Number: IRB00154198

- *Resilience* will be measured using the Connor-Davidson Resilience Scale. This is a 10 items self-report scale ask the participant to rate their opinion on the Likert scale range from 0 (not true at all) to 4 (true nearly all the time). This instrument has good internal consistency (Cronbach's alpha of 0.85) and constructs validity.
- *Well-being* will be measured using the Short-form survey (SF-36). This is a 36-items self-report instrument measure 2 domains: physical and affective well-being. SF-36 has good internal consistency (Cronbach's alpha ≥ 0.70).
- *Self-efficacy* will be measured by the coping self-efficacy (CSE) scale. The 13-items measure perceived self-efficacy for coping with challenges or threats. The CSE has a good internal consistency (Cronbach's alpha ranged from 0.8-0.91)
- *Sleep difficulty* will be measured by the Insomnia severity index. This 7 items questionnaire has acceptable reliability (Cronbach's alpha =0.73)
- *Fatigability or fatigue associated with specific physical activity* will be measured by the Pittsburg Fatigability Scale (PFS). The 10 items scale has strong internal consistency (Cronbach's alpha =0.88) and excellent rest-re-test reliability (interclass correlation 0.86).
- *MD Anderson Symptoms inventory* will be used to measure cancer related symptoms severity and interference. This 13-items questionnaire has acceptable reliability and validity.

Physiological and Biological Measurements

- *Physical activity (number of steps) and sleep duration* will be objectively measured by Fitbit Charge. This device can track 7 days of detailed motion, sleep, and physical activity data (e.g., steps, distance, active minutes, sleep duration, heart rate, and caloric usage) and store activity data in the Microsoft platform. Comparing the wearable devices (FitBit and Microsoft band 2) with the physical measurement gold standard (ActivPAL) in healthy participants during treadmill walking and during the free-living environment, the wearable device had an excellent agreement with the ActivPAL (Intraclass Correlation Coefficients = 0.81 and 0.96 respectively, $p < .01$).⁴⁹ When compared to the commercially available wearable devices (FitBit, Apple Watch, Garmin Vivofit and Microsoft Band 2), Fitbit has acceptable performance on the accuracy of the heart rate and precise calculation of carries burnt and distances.⁵⁰
- *Skeletal muscle strength* will be measured with a hand-held dynamometer. Grip strength will be measured on both hands in a neutral position of the arm, forearm, and wrist. Two consecutive attempts at 1-minute intervals will be measured. Each attempt will require a participant to exert a maximum possible grip force for about 5 seconds. After a minute of rest, the third attempt will measure fatigue resistance by asking the participant to hold the maximum hand grip as long as able until the 50% maximum grip force (based on the highest maximum handgrip force obtained from the first 2 attempts) is reached, which is often reached in less than a minute. The test will be repeated on the other hand. The same dynamometer will be used for all participants.
- *Plasma HSP90 and BDNF protein levels* will be measured by ELISA. ELISA will be performed according to the manufacturer's guide by one laboratory technician.

The physical performance will be measured using the short physical performance battery assessment (SPPB) and virtual SPPB (vSPPB) at baseline, 12 weeks at the program completion.

Date: September 26, 2024

Principal Investigator: [name]

Application Number: IRB00154198

Cognitive function will be measured by the Montreal Cognitive Assessment (MOCA) and the Multiple Ability Self-Report (MASQ) questionnaire. It is a 38-item measure that assesses 5 domains of perceived cognitive difficulties: language, visual perception, verbal memory, visual-spatial function, and attention/concentration.⁶⁴

HRV Data Collection:

An electrocardiogram approximately 5 minutes in length will be captured using the commercially available KardiaMobile ECG device (AliveCor, San Francisco, CA, USA). Participants will place their forefingers on the touchpad while seated and resting for the reading. Data will be captured using Kubios HRV software, a software tool for heart rate variability analysis (Kubios, Inc. Kuopio, Eastern Finland). Data will be analyzed by [name] (mentor for this project) who has extensive experience with both these technologies and has published on them.⁹ Differences between adjacent NN intervals will be assessed. Frequency domain analysis will be used to assess low-frequency power (LF power), high-frequency power (HF power), and the LF/HF ratio.

Magnetic Resonance Spectroscopy (MRS):

Before the first exercise intervention session, the diffusion-weighted (DW) imaging and ³¹P spectroscopy data will be collected using a 3T Philips Achieva MR scanner (Philips, Best, Netherlands) in the same imaging session. The data collection protocol and analysis will be done at NIA by [name] (The NIA Magnetic Resonance Spectroscopy expert) and his team.

Table 1: Data collection process

Tasks	Study visit 1	Weeks											Study visit 2
		1	2	3	4	5	6	7	8	9	10	11	
Screening: perceived exertion of 6MWT	X												
Demographic and disease information questionnaire	X												
FACT-F and PROMIS fatigue	X												X
PROMIS Adult profile	X												X
Cognitive function (MOCA and MASQ)	X												X
Physical activity (steps from the wearable device)*	X	X	X	X	X	X	X	X	X	X	X	X	X
Muscle strength test	X												X
Short-form survey (SF-36)	X												X
Connor-Davidson Resilience Scale	X												X
Coping self-efficacy scale	X												X
Pittsburg Fatigability Scale (PFS)	X												X
Physical performance (SPPB and vSPPB)	X												X
Heart rate variability	X												X
Blood sample for HSP90 and BDNF level	X												X
MRS for the central and peripheral markers (sub-study)	X												
Open-ended questions about the feasibility of the program													X

8. Risks

Date: September 26, 2024

Principal Investigator: [name]

Application Number: IRB00154198

Potential Risks and Protection Against Risks. Potential risks include (1) complications during the blood draw including pain and bleeding at the drawing site, (2) complications of the APA procedure, (3) minimum discomfort might occur while wearing the Fitbit charge (worn like a bracelet), (4) complications such as fainting or injury during the exercise program may occur. The MBI and responding to the questionnaires has no medical risk. The PI and research team plan to prevent the following risks:

1. Complications during the blood draw. Participants may experience pain and discomfort during the blood draw. They may also be at risk of bleeding. All blood draws will be performed by a certified phlebotomist. After the blood draw, participants' conditions will be monitored by a registered nurse (RN).
2. Complications of APA procedure: The auricular acupuncture procedure is considered safe with minimal risk. The most frequently reported adverse events were local skin irritation and discomfort, mild tenderness or pain, and dizziness. These events were transient, mild, and tolerable. Participants will be instructed to remove the tap with the seed when adverse events occur.
3. Minimum discomfort might occur while wearing the Fitbit charge (worn like a bracelet). Participants will be asked to wear a Fitbit to measure physical activity and sleep duration during their participation in the study. Participants will be instructed to take the band off when taking a shower. This equipment may cause discomfort. The material does not contain latex; however, the clasp is made of surgical grade stainless steel and contains traces of nickel, which may cause a rash. The device can be easily removed if discomfort is experienced. Participants will be asked to record the time and reason when and why they removed the band.
4. Complications (e.g., fainting, injury) during the exercise program. Participants will be instructed to walk and exercise at their own pace in the safety of their environment. All participants will be instructed to wear tennis shoes, comfortable clothing, and to eat a light snack before exercise.
5. The MBI and responding to the questionnaire has no medical risk. Participants will be asked to spend 20-30 min completing the questionnaire and listening to the instructions on how to use the smartphone application and Fitbit. All subjects will be informed that they can stop answering questions if they feel tired; they can resume the questionnaire at a later time. Participants will spend less than 5 min responding to a short survey on fatigue level, daily, through the application. Participation in this study involves the completion of questions (4 questions) about depressive symptoms. Scores from these questions (range from 4-20) would not be a sufficient basis for clinical decisions or diagnosis, contain substantial margins of error, and are not used for diagnostic purposes in this study. This score might hint at health conditions. Therefore, participants will receive the score for this depressive symptom subscale. If the depression score is higher than 16 (T score of > 70: severe depressive symptom), a registered nurse will suggest the participant discuss this issue with his/her primary health care provider.
6. Magnetic Resonance Spectroscopy (MRS)
There is a risk for injury from the magnetic resonance imaging (MRI) magnet if the participant has some type of metal in their body. It may be unsafe to have an MRI scan if the participant has a pacemaker or other implanted electrical device, brain stimulator, some types of dental implants, aneurysm clips (metal clips on the wall of a large artery),

Date: September 26, 2024

Principal Investigator: [name]

Application Number: IRB00154198

metallic prostheses (including metal pins and rods, heart valves, and cochlear implants), permanent eyeliner, implanted delivery pump, or shrapnel fragments.

Welders and metal workers may have small metal fragments in the eye. Each participant will be screened for such metal before having any scan. If the participant has any metal, they will not receive an MRI scan. If the participant has a question about metal in their body, they should inform the research team.

Each participant will be asked to complete an MRI screening form before each MRI scan. All magnetic objects must be removed before entering the MRI scan room. This includes items like watches, coins, jewelry, and credit cards.

It is not known if MRI is completely safe for a developing fetus. Therefore, female participants in childbearing age will have a pregnancy test done no more than 24 hours before each MRI scan. The scan will not be done if the pregnancy test is positive.

People with a fear of confined spaces may become anxious during an MRI. Those with back problems may have back pain or discomfort from lying in the scanner. The noise from the scanner is loud enough to damage hearing, especially in people who already have hearing loss. Everyone having a research MRI scan will be fitted with hearing protection. If the hearing protection comes loose during the scan, the participant should inform the research staff right away.

9. Benefits

There is no direct benefit to the participant from being in this study. However, the technology-enhanced home-based exercise (TEHE) program and the combination of the Acupressure and MBI with the TEHE programs proposed in this study could be used as choices for cancer survivors to manage their fatigue and improve patients' quality of life. The mEMA application and Fitbit will serve as useful tools for health care providers to monitor intervention outcomes and compliance.

10. Payment and Remuneration

Participants will receive a total of \$40 incentive and a Fitbit for completing 12 weeks program with 2 study visits and phone/video calls follow up. Participants who participate in the sub-study (MRS) will receive an additional of \$70 for participation.

If participants withdraw from the study before the 12 week, participants will be asked to return the device through the mail and there will be no penalties for withdrawal.

11. Costs

There will be no cost for participants to participate in this study.

12. Data Safety Monitoring Plan

This proposed study intends to evaluate the feasibility and preliminary efficacy of a 12-week technology-enhanced home exercise (TEHE) program and TEHE plus program with physical

Date: September 26, 2024

Principal Investigator: [name]

Application Number: IRB00154198

activity and fatigue; (2) explore the effect of the combined TEHE program with Acupressure and MBI on fatigue and physical activity; and (3) determine the effectiveness of the TEHE alone, TEHEplus, and MBI+TEHE programs on serum biomarkers (Heat Shock Protein 90 and Brain-Derived Neurotrophic Factor) compare to control (usual care) group. A Safety Monitoring Committee (SMC) will be formed, consisting of Johns Hopkins University clinician faculty members who are independent of this proposed feasibility study. The SMC will be responsible for overall monitoring of the safety of participants in this proposed study and overseeing the PI, Co-Is, and research assistant.

The PI will be responsible for managing all data, securing privacy and confidentiality, minimizing and identifying risks, monitoring and reporting adverse events or any safety issues, and complying with timely reporting requirements to all applicable regulatory bodies for any adverse events or unexpected problems. Monthly reports will be completed by the PI detailing participant demographics, recruitment status, treatment retention rates, protocol compliance, data gathered and accuracy, and quality assurance or regulatory issues that transpired, and summary of any adverse events. The research team (PI, Co-Is, and research assistant) will meet weekly via face to face or conference calling to discuss data and safety monitoring.

The SMC will meet annually (or more frequently if needed) and review the annual reports completed by the PI; review study safety, integrity, and progress including any adverse events; provide advice about continuing, changing, or terminating the study when necessary; require more frequent reporting as needed; audit the study for compliance and verify the authenticity of data, and assess that the research team is complying with informed consenting and other required regulations. These annual meetings will be conducted face-to-face or through conference calls.

References

1. National Cancer Institute. SEER Stat Fact Sheets: Prostate Cancer. 2007-2011. <http://seer.cancer.gov/statfacts/html/prost.html>; 2014.

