The feasibility of the TEHE plus program includes the evaluation of the recruitment and retention, acceptability, compliance, and delivery of the intervention. This study aims to measure the feasibility of the TEHE groups (including all five intervention arms). In the data collection process, the eligible participants recruited patients, a number of participants completing the intervention program will be recorded. Adherence to the intervention will be assessed using data collected from the activity tracker on minutes of moderate-intensity or greater activity. During the weekly exercise training, participants will discuss their home-based exercise barriers and potential solutions. At the end of the 12 weeks, participants will answer open-ended questions about their satisfaction and opinion about the programs (intervention groups) and the use of physical activity trackers and mobile phone application (control group).

By participating in the study, participants will spend 12 weeks, with 2 study visits. Participants will continue to receive their routine care and current therapy. They will continue with their therapy when the study ends or if the participation end prematurely. During the study, unexpected circumstances (e.g., worsening of cancer, extreme anemia, or another late side effect of cancer treatment). Participants will be removed from the study if his/her disease and/or condition is worsening.

Participants' personal information will be kept as private as possible and participants' names will not appear on any of the data forms. Blood sample tubes will be coded but de-identified and will be stored in locked freezers at Johns Hopkins School of Nursing biophysiological laboratory freezer until analyzed. Participants' health information will only be disclosed for this research study. Data will be stored for five years using assigned codes and will be kept on a password-protected computer held at the Johns Hopkins School of Nursing. Only study investigators will have access to the study data. After five years, the data will be shredded and discarded.

5. Inclusion/Exclusion Criteria

Exercise study:

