The mean and standard deviation of each outcome measure, recruitment rate, drop out, acceptability, tolerability will be calculated per group per study visit. The study primary aim the feasibility of a 12-week technology-enhanced home exercise (TEHE) program and TEHE plus program (***Aim 1***) will be analyzed using descriptive statistics of eligible participants and recruited participants, a number of participants completing the intervention program, compliance (number of participants complete the daily step goal), and participants' satisfaction and opinion of the intervention. To examine the effect of the TEHE program on fatigue, physical activity and serum biomarkers (Heat Shock Protein 90 and Brain-Derived Neurotrophic Factor) (***Aim 2***), the paired t-test will be used to analyze the effect of the program on fatigue, PA and biomarkers at the end of the program compared to baseline. The student t-test will be used to compare the variables among participants in the TEHE program, Acupressure only, TEHEplus, and TEHE +MBI compare to the usual care (control) group.

The secondary aims: The change of fatigue and physical activity level in week 12 compared to baseline will be calculated. Analysis of Variance (ANOVA) will be used to compare the effect of the TEHEplus, combined TEHE, and MBI with the TEHE only and Acupressure only on fatigue and physical activity (***Aim 3***). Change from baseline to 12 weeks will be computed for serum HSP90AA1 and BDNF levels. ANOVA will be used to examine the differences of change in serum biomarkers at week 12 compared to baseline in the TEHE only, Acupressure only, TEHEplus, TEHE +MBI and control (usual care) groups (***Aim 4***).

Sample size justification

Sufficient information from prior studies is not available for us to conduct a sample size calculation for the proposed multilevel analyses. The purpose of this pilot project is to explore the feasibility of the program and the relationships between the trajectories of the outcome measures, and not to achieve high power. The proposed N of 110 (22 participants/group) will likely result in low (below 0.60) statistical power. Results obtained will inform future power analyses for full-scale studies.

Early stopping criterion for safety/futility/efficacy as needed.

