The purpose of this pilot study is to examine the feasibility of the interventions. Therefore, participants may be asked to stop their participation early if there are serious complications include metastasis of the disease is found, serious injuries (broken bone, severe muscle injury) that prohibit the participants to exercise, severe infection during the 12 weeks intervention (e.g., fever, redness, swelling, etc.).

Inclusion and exclusion criterion: please see section 5.

Intervention/Independent Variables.

Technology-Enhanced Home Exercise (TEHE) Program: An online individual exercise session will be offered at the first study visit. Participants will be complete an exercise training program (45-60 min) to reach a moderate intensity using the heart rate monitor and exertion level.

The online exercise training/consultation program will include

- Goal setting/discussion of the progress (25 min): Participants will spend 25 min to discuss the physical activity barriers and set up a goal for the program.
- Exercise safety and body alignment (10 min): Participants will learning about posturing and body alignment to maintain their safety during exercise and monitoring the heart rate using the wearable device.
- Review physical activity and symptoms (15 min)
- At the end of the program, participants will select follow up methods (phone or video call), reminder message scheduled time and frequency.

At home: Participants will receive a weekly recommendation through a smartphone application and be instructed to follow their physical activity/step goals. Participants will receive a summary report of their weekly physical activity and symptoms (Fitbit and mobile phone application data).

The PI ([name]) will monitor the intervention session to ensure intervention fidelity. Adherence to the intervention will be assessed by data collected from the activity tracker on minutes of moderate-intensity or greater activity. At the end of the 12 weeks, participants will answer open-ended questions about their satisfaction with the program.

The Acupressure program: Participants in this group will receive online or in person auricular point acupressure (APA) and body pressure points training at the first study visit. An online educational video and written material developed by interventionists and PI, will

Figure 3. Ear Points for Fatigue

Date: September 26, 2024

Principal Investigator: [name]

Application Number: IRB00154198

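### Participants who worsen are removed under two conflicting rules with no stated follow-up, so the week-12 tests would most naturally run only on those who did not worsen

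*Combined protocol and SAP*

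**What the plan says.** Two passages govern early exit.

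- **Section 4, Study Procedures** (closing paragraphs under Randomization) gives examples of "unexpected circumstances (e.g., worsening of cancer, extreme anemia, or another late side effect of cancer treatment" and then a mandatory rule: "Participants will be removed from the study if his/her disease and/or condition is worsening". Worsening is not defined further.
- **Section 7, early stopping criterion**, is permissive: "participants may be asked to stop their participation early if there are serious complications include metastasis of the disease is found". It adds "serious injuries (broken bone, severe muscle injury) that prohibit the participants to exercise" and severe infection.

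The Section 7 analysis plan depends on week-12 values. Aim 2 has a within-arm part: "the paired t-test will be used to analyze the effect of the program on fatigue, PA and biomarkers at the end of the program", with baseline as the reference. For the comparison with usual care, "The student t-test will be used to compare the variables among participants in the TEHE program" and in the other active arms. For Aim 3, "The change of fatigue and physical activity level in week 12 compared to baseline will be calculated" and compared by ANOVA; Aim 4 treats the biomarkers in the same way.

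Table 1 schedules FACT-F and PROMIS fatigue only at study visits 1 and 2. Section 10 asks participants who withdraw before week 12 to mail the Fitbit back. Drop-out is to be summarised per group. No analysis set, missing-data method or sensitivity analysis is given. The sample size paragraph mentions multilevel analyses, but the analysis plan specifies none.

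**The concern.** The Section 4 rule takes the participant out of the study, not only out of the intervention, and it is triggered by health during follow-up. Its examples (progressing cancer, extreme anemia, late treatment effects) are plausibly tied to fatigue and activity, which are Aim 2 outcomes. If those participants have no week-12 value, every planned test is restricted to people who did not worsen.

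Two things are at stake. A within-arm change estimated only in those who stayed well can look better than the change in everyone randomised. A comparison with usual care can be distorted if the arms lose different numbers or different kinds of participants. The Section 7 injury trigger refers to being unable to exercise, and three of the five arms receive the exercise program, so unequal loss is possible. The effect against usual care is a primary aim, and the results are meant to feed later power calculations, so a shifted estimate would be carried forward.

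**Working it through.** **The plan's own figures.** The plan gives no removal or drop-out rate, so there is none to reproduce. Its one statistical figure is power below 0.60 with 110 participants (5 × 22). With no effect size, SD or alpha stated, that can only be bracketed: at two-sided 0.05 and 22 per arm, power is 0.37 for a difference of 0.5 SD and 0.58 for 0.67 SD. The statement is consistent with moderate effects.

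**The two rules side by side.**

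| | Section 4 | Section 7 |
|---|---|---|
| Force | mandatory | permissive |
| Triggers | worsening disease or condition; examples are cancer, anemia, late effects | metastasis, injury preventing exercise, severe infection |
| Outcomes afterwards | not stated | not stated |

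**Within-arm shift.** Assume a share q of an arm is removed, being the worst on a normally distributed measure of worsening that has correlation ρ with a poor outcome change. The mean of those retained then moves toward improvement by

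shift = ρ × φ(z) / (1 − q) in SD units, where z is the (1 − q) normal quantile.

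For q = 0.10: z = 1.282, φ(z) = 0.1755, and 0.1755 / 0.90 = 0.195. Multiplying by 0.6 gives 0.117.

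| Assumed share removed | ρ = 0.6 | ρ = 1 (upper bound) |
|---|---|---|
| 5% | 0.07 SD | 0.11 SD |
| 10% | 0.12 SD | 0.20 SD |
| 15% | 0.16 SD | 0.27 SD |
| 20% | 0.21 SD | 0.35 SD |

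Simulation (22 per arm, no true change, 10% removed, two-sided 0.05): the paired t-test rejects in 7.2% of trials at ρ = 0.5, 8.8% at ρ = 0.7 and 14.0% at ρ = 1.

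**Between-arm bias, no true effect.**

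- Equal removal, 10% in each arm: bias about 0, rejection about 5%.
- Control 5%, intervention 15% (22 per arm): +0.08 SD and 5.8% rejection at ρ = 0.5; +0.17 SD and 9.1% at ρ = 1. Swapping the rates reverses the sign.
- 5% in one arm, 20% in the other (21 per arm, from the abstract's 105 / 5): the formula gives 0.350 − 0.109 = 0.241 SD at ρ = 1, and 0.6 × 0.241 = 0.145 SD at ρ = 0.6. Simulation gives 0.241 SD with 12.7% rejection and 0.144 SD with 7.1%.

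Unequal removal favours the arm that loses more participants.

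**Between-arm bias, true benefit of 0.5 SD.** With one removal threshold for both arms and 10% of controls removed, the estimate falls to 0.47 SD (ρ = 0.5) or 0.39 SD (ρ = 1). Power falls from about 0.37 to 0.32 or 0.28. Here the bias works against the intervention.

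**The case against.** The strongest reply is that several tempting readings go beyond the text.

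- *The plan says outcome collection ends at removal.* A reader might infer this, but the documents do not say it. It follows from being taken out of the study together with a two-visit questionnaire schedule. The device-return sentence in Section 10 concerns participants who withdraw, not those who are removed. The inference is the natural one, and nothing contradicts it, but it remains an inference.
- *Removal selects on the outcome itself.* It does not. The triggers are medical events, and none is a FACT-F, PROMIS or step-count threshold. The ρ = 1 figures are therefore only an upper bound.
- *Every paired t-test will look like improvement.* This is not supported for the biomarkers. Section 3 describes BDNF as low in chronic fatigue yet activated under stress, so the direction there is unclear. For fatigue and activity, a shift of about 0.1 SD need not turn a decline into a gain.
- *The comparison with usual care is biased in favour of the intervention.* The direction is not fixed, and under equal removal with no effect there is essentially no bias.

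Size can also be questioned. A 5% versus 20% split within 12 weeks is a marked contrast in people selected for walking ability and no active infection. The standard error of a difference at 21 per arm is √(2/21) = 0.31 SD, larger than the 0.24 SD upper-bound bias. Controls also wear the Fitbit and report symptoms daily, so closer observation of the active arms is a weak argument. Removals that lower retention are what a feasibility aim should record, not a distortion of it.

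All of this limits the size and certainty of the problem. It leaves standing the conflict between the two rules, the silence on follow-up after removal, and the absence of an analysis set.

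**Conclusion.** The concern holds in a limited form. The two removal rules conflict in force and in triggers. Followed as written, the plan most naturally confines its week-12 t-tests and ANOVAs to participants who did not worsen. Changes in fatigue and activity within an arm then shift toward apparent improvement, by about 0.12 SD if 10% are removed at correlation 0.6, with 0.20 SD as the upper bound. Comparisons with usual care can be biased when removal differs by arm or treatment has an effect, in a direction that cannot be fixed in advance. The 5% versus 20% case (0.14 SD and 7% rejection; upper bound 0.24 SD and 13%) is an illustration, not a forecast.

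These figures rest on assumed removal rates and correlations, a normal model, a two-sided 0.05 test, and the inference that removed participants have no week-12 value. The trial is a low-powered pilot, which reduces the consequence. Because the effect against usual care is a primary aim and the remedy is cheap, the change should still be made.

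**What to change.** 1. Reconcile the Section 4 rule with the Section 7 early-stopping paragraph. Which clinical rule applies is for the sponsor to decide.
2. State that stopping the intervention does not end outcome follow-up. Unless consent is withdrawn, seek the week-12 FACT-F and PROMIS questionnaires remotely through REDCap, which the study already uses.
3. Keep Fitbit data already collected, and clarify that the device return in Section 10 applies to withdrawal from the study.
4. Analyse participants in the arm to which they were randomised, using all week-12 outcomes obtained.
5. Report the number of removals and their reasons by arm, so that readers can judge any remaining imbalance.

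The cost is protocol and consent wording plus a few remote questionnaires, with no extra visits. The downside is a small burden on participants who are unwell, and some will decline. Blood biomarkers need an in-person draw and may still be missing after removal, so this reduces the bias for fatigue more than for HSP90 and BDNF.
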